4.2.8. Integrated Genomics

By virtue of collection of both DNA and blood cell RNA from a large number of well-characterized participants with COPD (GOLD II-IV), smokers without COPD, and healthy non-smokers, the SPIROMICS study will provide a new opportunity to explore a "systems biology" approach to COPD (see Figure 1). Additional insights provided by proteomic and metabolomic analyses will add further power.

It is widely believed that genetic modifiers that predispose individuals to, or protect from, development of COPD and predict degree of disease severity will provide insight into specific molecular pathways that may contribute to specific subsets of patients with the disease. Recent work has implicated α -nicotinic acetylcholine receptor (CHRNA3/5), hedgehog interacting protein (HHIP), and SERPINE2 (Pillai et al, 2009; Zhu et al.2007) as well as other genetic variants identified by candidate gene studies that either interact with tobacco smoke (IL13, Sadeghnejad et al.; 2007) or affect pulmonary function in participants with COPD such as ADAM33 (Sadeghnejad et al.; 2009). Additionally, there is a high likelihood that additional modifiers will be identified based upon larger, more comprehensive studies, such as the COPD Foundation funded initiative known as COPDGene, which will data from over 10,000 COPD participants.

The great advantage of the SPIROMICS study will be the ability to relate these genetic polymorphisms to gene expression, protein expression, and aspects of cellular inflammation in the lungs of affected patients. In addition, the use of lung tissue specimens will allow assessment of epigenetic changes, which are likely to be important in this disease which has a prominent environmental component. The integrated analysis of these genomic data will comprise a cutting-edge approach to the identification of disease-relevant molecular pathways (see Figure 2). The use of blood cells for gene expression and miRNA analyses has some ancillary value in: 1) phenotyping participants based on the systemic, inflammatory component of the COPD phenotype, and 2) the potential to develop non-invasive tests for specific molecular phenotypes.

Figure 2. Genomic Analyses and Systems Biology

5. Study Design

[figure not shown]
5.1. Overview or Design Summary

SPIROMICS is a prospective cohort study that will enroll approximately 3,200 participants at six clinical centers with a total of 11 recruitment locations over three years. All participants will have up to four main study-related visits (Baseline and Follow-up visits at years 1, 2, and 3 post-baseline). During the study visits, clinic staff conduct physical examinations and tests, collect biological specimens, and administer a series of questionnaires to study participants. Participants also receive quarterly follow-up calls to assess health status and determine if an exacerbation has occurred.

5.2. Schedule of Study Contacts

Figure 3 depicts the schedule of clinical visits and follow-up calls in SPIROMICS.

Figure 3. Schedule of Study Contacts

5.3. Participant Selection and Withdrawal

5.3.1. Inclusion/Exclusion Criteria

The 3,200 participants will be distributed across four enrollment strata (i.e., Non-smokers, Smokers without COPD, Mild/Moderate COPD, and Severe COPD) as shown in Table 1. Participants must fall into one of the four categories described in Table 1 in addition to meeting the inclusion/exclusion criteria described Section 5.3.1, 5.3.1.1, and 5.3.1.2 in order to be included in the study. With regards to race/ethnicity, sites' recruitment will reflect national racial distributions. All centers will recruit equal numbers of males and females.

Table 1. SPIROMICS Enrollment Strata

	Non-Smokers (Stratum 1)	Smokers (Stratum 2)	Mild/Moderate COPD (Stratum 3)	Severe COPD (Stratum 4)
Smoking Status	< 1 pack-year	> 20 pack-years	> 20 pack-years	> 20 pack-years
Bronchodilator Status for Assessing Lung Function	Pre-bronchodilator	Post- bronchodilator	Post-bronchodilator	Post-bronchodilator
FEV ₁ /FVC ratio criteria	FEV ₁ /FVC > .7	FEV ₁ /FVC > .7	FEV ₁ /FVC < .7	FEV ₁ /FVC < .7
Other Lung Function Criteria	FVC>LLN	FVC>LLN	FEV ₁ > 50% pred.	FEV ₁ < 50% pred.
Sample Size	N = 200 (6.25%)	N = 900 (28.13%)	N = 1500 (46.88%)	N = 600 (18.72%)

Regarding participation in other studies:

1. Participants may participate in concurrent observational studies, excluding the COPDGene Study (COPDGene Investigators, 2010)
2. Participants in therapeutic clinical trials can be included after the treatment is unmasked.
3. Participants in ongoing, open-label clinical trials can be enrolled if the participant is in the control group of such a study.
4. Participants recruited into SPIROMICS can be recruited into other interventional studies after SPIROMICS baseline values are obtained. Clinic staff will maintain records documenting activity in interventional studies.

5.3.1.1. Inclusion/exclusion criteria

Table 2. Inclusion/Exclusion Criteria

	Non-smokers	Smokers	Mild/Mod COPD	Severe COPD
Inclusion Criteria				
Between age 40 and 80 (inclusive) at Baseline Visit	X	X	X	X
Able to tolerate and willing to undergo study procedures	X	X	X	X
<1 pack-year history of smoking	X			
>20 pack-year history of smoking		X	X	X
Pre-bronchodilator: FEV ₁ /FVC ≥.7 and FVC>LLN	X			
Post-bronchodilator: FEV ₁ /FVC ≥.7 and FVC>LLN		X		
Post bronchodilator: FEV ₁ /FVC < .7 and FEV ₁ > 50% pred			X	
Post bronchodilator: FEV ₁ /FVC < .7 and FEV ₁ < 50% pred				X
Able to understand English and/or Spanish	X	X	X	X
Exclusion Criteria				
Women only: Cannot be pregnant at baseline or plan to become pregnant during the course of the study	X	X	X	X
Dementia or other cognitive dysfunction which in the opinion of the investigator would prevent the participant from consenting to the study or completing study procedures	X	X	X	X
Has plans to leave the area in the next 3 years	X	X	X	X
Smoking history of > 1 pack-year but <21 pack-years	X	X	X	X
Has a BMI > 40 kg/m ² at baseline exam	X	X	X	X
Prior significant difficulties with pulmonary function testing	X	X	X	X
Hypersensitivity to or intolerance of albuterol sulfate or ipratropium bromide or propellants or excipients of the inhalers	X	X	X	X
Non-COPD obstructive lung disease (various bronchiolitis, sarcoid, LAM, histiocytosis X) or parenchymal lung disease, pulmonary vascular disease, pleural disease, severe kyphoscoliosis, neuromuscular weakness, or other conditions, including clinically significant cardiovascular and pulmonary disease, that, in the opinion of the investigator, limit the interpretability of the pulmonary function measures.	X	X	X	X
History of Interstitial lung disease	X	X	X	X
Current diagnosis of asthma	X			
History of Lung volume reduction surgery or lung resection	X	X	X	X
History of lung or other organ transplant	X	X	X	X
History of endobronchial valve therapy	X	X	X	X
History of large thoracic metal implants (e.g., AICD and/or pacemaker) that in the opinion of the investigator limit the interpretability of CT scans	X	X	X	X
Currently taking ≥10mg a day/20mg every other day of prednisone or equivalent systemic corticosteroid	X	X	X	X
Currently taking any immunosuppressive agent	X	X	X	X
Current illicit substance abuse, excluding marijuana	X	X	X	X
History of or current use of IV Ritalin	X	X	X	X
History of or current use of heroin	X	X	X	X
History of illegal IV drug use within the last 10 years or more than 5 instances of illegal IV drug use ever	X	X	X	X
Known HIV/AIDS infection	X	X	X	X
History of lung cancer or any cancer that spread to multiple locations in the body	X	X	X	X
History of or current exposure to chemotherapy or radiation treatments that, in the opinion of the investigator, limits the interpretability of the pulmonary function measures.	X	X	X	X
Diagnosis of unstable cardiovascular disease including myocardial infarction in	X	X	X	X

the past 6 weeks, uncontrolled congestive heart failure, or uncontrolled arrhythmia				
Any illness expected to cause mortality in the next 3 years	X	X	X	X
Active pulmonary infection, including tuberculosis	X	X	X	X
History of pulmonary embolism in the past 2 years	X	X	X	X
Known diagnosis of primary bronchiectasis	X	X	X	X
Currently institutionalized (e.g., prisons, long-term care facilities)	X	X	X	X
Known to be a first degree relative of another, already enrolled participant (i.e., biological parent, biological sibling)	X	X	X	X

5.3.1.2. Temporary exclusion criteria

Temporary exclusion criteria are events, diseases, or treatments that require a waiting period to elapse before a participant can be screened for SPIROMICS. In addition, these criteria should be applied when scheduling the Years 1, 2, and 3 visits.

- Participants who present with a pulmonary exacerbation, either solely participant-identified or that has been clinically treated, in the last six weeks can be rescreened for the study once the six-week window has passed.
- Participants who present with an upper respiratory infection, either solely participant-identified or that has been clinically treated, in the last six weeks can be rescreened for the study once the six-week window has passed.
- Participants who present with current use of acute antibiotics or steroids can be rescreened for the study ≥ 30 days after discontinuing acute antibiotics/steroids. This does not apply to participants who are on chronic prednisone therapy of < 10 mg per day or < 20 mg every other day or participants who are currently on chronic, prophylactic, or suppressive antibiotic therapy.
- Participants who are currently on chronic, prophylactic, or suppressive antibiotic therapy must have started this therapy at least 6 weeks prior to the baseline visit.
- Participants who present with a myocardial infarction or eye, chest or abdominal surgery within six weeks can be rescreened after the six week window has passed. Study coordinators should consult with the site principal investigator prior to rescreening these participants.
- Female participants who present < 3 months after giving birth will be asked to reschedule their visit until three months have passed since the birth.

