6.2. Schedule of Measurements

Table 3. Schedule of Study Measurements

	V1	V2	V3	V4
Physiological Measures				
Pulmonary Function Testing				
Exhaled CO (eCO)	X	X		X
Forced Vital Capacity	X	X	X	X
Slow vital capacity	X	X	X	X
Bronchodilation	X	X	X	X
Forced Vital Capacity	X	X	X	X
Slow Vital Capacity	X	X	X	X
Six minute walk test with continuous pulse oximetry	X	X	X	X
Anthropometric Measurements				
Height	X	X	X	X
Weight	X	X	X	X
Arm Span	X	X	X	X
Waist	X	X	X	X
Hip	X	X	X	X
Neck	X	X	X	X
Seated Blood Pressure	X	X	X	X
MDCT	X	X		
Biospecimen collection				
Blood				
Serum (Two - RT)	X	X		X
Plasma (One - P100)	X	X		X
Plasma (Three - Plasma/DNA w/EDTA and One CBC w/EDTA)	X	X		X
Plasma (One –with citrate)	X	X		X
RNA (One – PAX - Gene)	X	X		
Urine	X	X		X
Induced Sputum	X	X*	X*	X*
Questionnaires				
Medical History	X	X	X	X
St. George’s Respiratory Questionnaire	X	X	X	X
MOT Short Form – 12	X	X	X	X
COPD Assessment Test	X	X	X	X
Modified Medical Research Council (MRC) Dyspnea Scale	X	X	X	X
Sleep questionnaires				
Berlin Questionnaire	X	X	X	X
Pittsburgh Sleep Quality Index	X	X	X	X
Veterans Specific Activity Questionnaire	X	X	X	X
Hospital Anxiety and Depression Scale (HADS)	X	X	X	X
FACIT	X	X	X	X
Questionnaire for Ease of Cough and Sputum Clearance	X	X	X	X

*Sample collection attempted only if initial collection at baseline failed.

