7.3. Analysis Plan

Data analyses will be conducted in SPIROMICS with the overarching goal of achieving the two primary study objectives, namely, the identification of homogenous subgroups of COPD patients and the identification of potentially useful intermediate outcomes, both of which can inform future therapeutic clinical trials with an emphasis on trials conducted for regulatory approval. The data planned for collection in SPIROMICS are extensive and involve fairly complex data structures. Numerous specific hypotheses directed at both general study aims will be evaluated. Detailed statistical analysis plans will be developed for each specific hypothesis describing the methods to be used for data analysis and addressing issues such as missing data and multiplicity of statistical testing.

Hypothesis # 1 -- Subgroup Identification: Three different approaches will be taken to subgroup finding. The first assumes that homogeneous subgroups can be defined in terms of multiple measurement domains (including clinical, radiological, proteomic, and genomic) through the application of statistical techniques, such as hierarchical cluster analysis, described in Sections 7.4.1 and 7.4.2. Discovery of novel clustering or classification schemes is the goal of analyses conducted with this approach, therefore it is difficult to specify a priori hypotheses to be evaluated. Examples, however, can be provided, such as:

- Clusters of participants will be defined based on genome-wide genetic, epigenetic, and gene expression data that share molecular pathways of disease and are therefore useful in guiding development of targeted therapeutic approaches.
- Homogeneous subgroups of patients will be identified according to their ‘sputum footprint,’ defined as mucin concentration, microbiome content, and neutrophil concentration, that will provide novel groupings of disease severity and therefore be useful for targeted enrollment in future clinical trials.

Because this approach involves discovery of novel subgroups rather than confirmation of a priori hypothesized subgroups, cross-validation methods to assess the predictive power of a particular subgroup classification scheme will be invoked.

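### The acute antibiotic/steroid washout in Section 5.3.1.2 is triggered only by current use, so a non-respiratory course that has just ended does not defer the visit, and its exemption is worded by participant rather than by drug

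*Protocol*

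**What the plan says.** Section 5.3.1.2 opens by describing temporary exclusions as events, diseases or treatments after which some time must pass before screening. It says that the same criteria apply when the Year 1, 2 and 3 visits are scheduled.

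The bullets are triggered in different ways:

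- **Exacerbation:** a six-week look-back, "Participants who present with a pulmonary exacerbation, either solely participant-identified or that has been clinically treated, in the last six weeks". The upper respiratory infection bullet has the same form, and the bullet on myocardial infarction and surgery also looks back six weeks.
- **Acute antibiotics or steroids:** current use only, "Participants who present with current use of acute antibiotics or steroids can be rescreened for the study". The wait is at least "30 days after discontinuing acute antibiotics/steroids".
- **Exemption from the antibiotic/steroid bullet:** "This does not apply to participants who are on chronic prednisone therapy of < 10 mg per day" (or the stated alternate-day equivalent), and likewise "participants who are currently on chronic, prophylactic, or suppressive antibiotic therapy".

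The neighbouring entries in Table 2 (Section 5.3.1.1) also concern the present only: systemic corticosteroid currently taken at or above 10 mg a day or 20 mg every other day, and active pulmonary infection.

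For induced sputum after baseline, the footnote to Table 3 (Section 6.2) says "Sample collection attempted only if initial collection at baseline failed". Section 7.3 gives as an example of subgroup finding a sputum footprint "defined as mucin concentration, microbiome content, and neutrophil concentration".

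**The concern.** The bullet itself treats the 30 days after the last dose as a period in which a participant should not be assessed. Its trigger does not protect that period for anyone whose course is already over. Two people one day apart at the end of the same course are handled in opposite ways: the one still on drug is sent away for 30 days, and the one who has just stopped proceeds. That runs against the section's stated purpose.

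Sputum microbiome, sputum neutrophils and blood inflammatory markers are inputs to subgroup finding and to the search for intermediate outcomes, and they are plausibly altered by recent antibiotics or steroids. Sputum is repeated only if the baseline attempt failed, so a specimen taken just after treatment normally remains that participant's only one. Blood is taken at baseline, Year 1 and Year 3, so a badly timed draw can also enter a change from baseline to Year 1, which Section 7.4.3 names as a form of intermediate outcome.

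**Working it through.** The protocol states no figure on this point, so there is none to reproduce. The check has three steps.

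**1. What the other bullets already cover.** Inputs from Section 5.3.1.2: a six-week hold (42 days) for exacerbations and upper respiratory infections, treated or not, and a 30-day washout. Assumptions: the 42 days run from onset, treatment starts at onset, and a course lasts L = 5 to 14 days (the protocol gives no course length). Days off drug when the hold ends = 42 − L.

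| L (days) | Days off drug at day 42 |
|---|---|
| 5 | 37 |
| 7 | 35 |
| 10 | 32 |
| 14 | 28 |

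The 30-day aim is met for L up to 42 − 30 = 12 days, and a 14-day course falls 2 days short. Courses for these two conditions are therefore essentially protected. What is left is acute courses for any other reason. Section 6.7.2.1 defines an exacerbation as one of COPD, so treatment of a resolved lower respiratory infection in the two strata without COPD (200 + 900 = 1,100 participants) arguably belongs here too.

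**2. How many visits the remaining gap could touch.** If such courses end at rate r per person-year, the chance that a visit falls within 30 days after the end of one is 1 − exp(−r × 30/365). The range of r is an assumption.

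- r = 0.2: 1 − exp(−0.01644) = 1.6%, or 52 of 3,200 baseline visits.
- r = 0.8: 1 − exp(−0.06575) = 6.4%, or 204 of 3,200.

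These are counts of visits. The number of sputum specimens would be smaller, because Section 6.4.6.2.2 bars induction when post-bronchodilator FEV₁ is below 35%.

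**3. What the exemption releases.** Its subject is the participant on chronic therapy. Read literally, someone on long-term antibiotics who is now taking a separate acute course is outside the bullet. At baseline, Table 2 still excludes current steroid use at or above its threshold, with no exception for chronic therapy. The exacerbation and upper respiratory infection bullets have no exemption either. The baseline remainder is therefore mainly acute antibiotics for other reasons, plus steroid courses below the Table 2 threshold. Section 5.3.1.2 carries only the temporary criteria forward to Years 1 to 3, so the Table 2 backstop is not stated to apply at those visits.

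**The case against.** The strongest answer is that the section works as a whole. In a COPD cohort, exacerbations and respiratory infections are an obvious reason for acute antibiotics or steroids, and the six-week bullets hold those participants whether or not they are on chronic therapy. The opening sentence makes the intent plain, so a coordinator could well apply the 30 days to a course that has just ended. The exemption can be read as a clarification that chronic therapy does not count as acute use. Treatment for exacerbations is also asked about during follow-up (Sections 6.7.2.1 and 6.7.2.3), so some exposure before later visits is on record.

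Much of this stands, and it rules out two stronger readings.

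- **That most of the targeted exposure gets through.** A reader might take the bullet alone, note that it catches L days out of L + 30, and conclude that 30/(L + 30) is missed: 86% for a 5-day course and 68% for a 14-day course. That ignores the six-week bullets. If a share f of courses is for the two respiratory conditions, the missed share is [(1 − f) × 30 + f × max(0, L − 12)]/(L + 30). It falls below half once f exceeds about 0.42 (5 days), 0.38 (7 days), 0.33 (10 days) or 0.29 (14 days), and at f = 0.8 it is 15% to 17%. The protocol does not give f.
- **That the error differs by severity stratum.** A reader might infer this from heavier treatment in sicker participants. Exacerbation treatment is already held by the six-week bullet, and nothing in the protocol shows that other courses become more frequent with COPD severity.

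The appeal to intent does not close the gap. If some sites apply the bullet as a look-back and others as written, the rule is not uniform.

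**Conclusion.** The point holds as a wording fault with a limited reach. As written, an acute course that ended within the last 30 days, and was not for an exacerbation or upper respiratory infection in the last six weeks, does not defer the visit. The same course still in progress does. The exemption is also broader than its evident purpose.

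The size cannot be taken from the protocol. The estimate of 1.6% to 6.4% of visits rests wholly on the assumed 0.2 to 0.8 uncovered courses per person-year. The finding that respiratory courses are nearly all covered rests on counting six weeks from onset, with treatment starting then. The change is worth making because the bullet as worded defeats the section's own purpose and the sputum specimen is normally not repeated. It does not show that the washout as a whole fails.

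**What to change.** Reconcile the trigger with the interval already in the bullet. Deferral should apply to acute antibiotics or steroids in current use and to any such course that ended within the existing 30 days, at screening and at the Year 1, 2 and 3 visits. Word the exemption so that it covers only the chronic drug itself and not a separate acute course in the same participant. No new interval or dose threshold is needed.

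The cost is a sentence or two in Section 5.3.1.2 and a screening-form item for the date of the last dose. A small share of visits would be delayed by up to 30 days, about 1.6% to 6.4% under the assumption above.

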4.1.3.1. BODE Index

Several variables, such as BMI (body mass index), dyspnea, and FEV₁, are known to be predictors of mortality in COPD patients, but the relative strength of each individual variable remains difficult to determine. Recent data suggest that the BODE index, can be useful and predict changes in prognosis (Cote, 2005; Imfeld et al, 2006). This is an index that takes into account body mass (B), obstruction (O), dyspnea (D) and exercise endurance (E). Use of this index in the context of SPIROMICS is in line with the overall philosophy to utilize multiple parameters to define patient disease status. This index will be calculated for the Year 3 visit for use as a long-term clinical endpoint.

4.2. Rationale for the Selection of Assessments to Define Phenotypes and Ascertain Intermediate Outcome Measures

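### Section 5.3.1.2 ties the chronic-antibiotic start window to the baseline visit even when scheduling Years 1 to 3, so anyone who starts such therapy after baseline literally cannot be scheduled while on it

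*Protocol*

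**What the plan says.** Section 5.3.1.2 presents temporary criteria as conditions that a delay will clear, and then extends them beyond entry: "these criteria should be applied when scheduling the Years 1, 2, and 3 visits". Three provisions bear on the point.

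- **The 30-day bullet.** "Participants who present with current use of acute antibiotics or steroids can be rescreened for the study" once at least 30 days have passed since stopping. It has two exemptions in one sentence: "This does not apply to participants who are on chronic prednisone therapy of < 10 mg per day or < 20 mg every other day", followed by "or participants who are currently on chronic, prophylactic, or suppressive antibiotic therapy".
- **The next bullet.** People currently on chronic, prophylactic or suppressive antibiotics "must have started this therapy at least 6 weeks prior to the baseline visit". No other visit is mentioned.
- **Table 2 (Section 5.3.1.1).** Current prednisone (or equivalent) at 10 mg a day or 20 mg every other day and above is an entry exclusion. It is not on the temporary list.

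On outcomes, Section 7.4.3 names all-cause mortality, exacerbations and FEV1 decline over three years as the primary clinical endpoints. Section 4.1.3.1 says of BODE: "This index will be calculated for the Year 3 visit for use as a long-term clinical endpoint". Table 3 places CT at baseline and Year 1 only, and blood and urine at baseline, Year 1 and Year 3.

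**The concern.** A criterion meant to postpone a visit becomes, for one group, a bar that waiting cannot lift. It also defeats the bullet above it, which takes long-term antibiotic users out of the 30-day deferral, presumably so that they can be seen.

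The measurements at risk are those that need a clinic visit: FEV1 decline, Year 3 BODE, and the baseline-to-Year 1 changes that Section 7.4.3 gives as an example of an intermediate outcome. If starting such therapy is related to disease course, those measurements would be missing for a reason tied to the outcome. The same participants would go on contributing exacerbations through the quarterly calls (Section 6.5.1) and deaths through calls and the annual National Death Index search (Section 6.7.1). Section 7.1 assumes the same 92% retention among survivors in both COPD strata, so the plan makes no allowance for differential loss of this kind.

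**Working it through.** **1. Does waiting ever satisfy the rule?** Let T be the week in which therapy starts, counted from baseline, and V the week of the visit being scheduled.

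- Rule as written: T ≤ −6. V does not appear, so with T > 0 the condition fails at every V.
- Rule anchored to the visit: V − T ≥ 6. This is met after six weeks.

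Example: therapy starts at month 18 and continues. At Year 2 it has run about 26 weeks, and at Year 3 about 78 weeks. The written rule fails at both visits; the visit-anchored rule is met at both. The bullet covers current users, so the bar lasts as long as the therapy does.

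**2. What is lost?** A participant who starts before Year 1 and continues loses the Year 1 CT, the Year 1 biospecimens and all later FEV1 values. One who starts at month 18 keeps baseline and Year 1 data but loses Year 2 and Year 3 spirometry, Year 3 BODE and Year 3 blood and urine. Exacerbation counts and vital status are kept in both cases.

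**3. Power for FEV1 change (Section 7.1).** Inputs: 1,500 Mild/Moderate and 600 Severe; deaths 10% and 15%; 92% retention of survivors; difference 0.20 SD; two-sided alpha 0.05.

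- n1 = 1500 × 0.90 × 0.92 = 1242; n2 = 600 × 0.85 × 0.92 = 469.2
- Power = Φ(0.20 / √(1/n1 + 1/n2) − 1.96) = Φ(3.69 − 1.96) = 95.8%, against about 95% stated. The plan's figure reproduces.

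The extra losses of Year 3 FEV1 below are assumptions, because the protocol gives no start rate:

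| Extra loss, Mild/Moderate | Extra loss, Severe | Power |
|---|---|---|
| 0% | 5% | 95.2% |
| 5% | 10% | 94.1% |
| 5% | 20% | 92.2% |
| 10% | 20% | 91.8% |
| 10% | 30% | 89.0% |

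**4. Bias from informative loss.** If a fraction f of the Severe stratum is missing and its mean change is d SD worse than that of the rest, the observed stratum mean is off by f × d. Both inputs are assumed.

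| f | d = 0.25 SD | d = 0.50 SD |
|---|---|---|
| 5% | 0.0125 | 0.025 |
| 10% | 0.025 | 0.05 |
| 20% | 0.05 | 0.10 |

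The largest value is half of the 0.20 SD target difference.

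**5. The steroid wording.** If the word acute governs both drug classes in the 30-day bullet, chronic prednisone is outside it at any dose, and the low-dose exemption has nothing to do. If acute governs antibiotics only, chronic prednisone at or above the exempted dose defers the visit until at least 30 days after stopping. At entry the choice does not matter, because Table 2 already excludes those doses. At follow-up it does, and the text does not settle it.

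**The case against.** The best reply is that no site would apply the bullet literally. It names only the baseline visit, so it can be read as a baseline condition, and the exemption above it would then admit long-term antibiotic users at follow-up. Alternatively it can be read as six weeks before whichever visit is due, which fits the notion of a waiting period. On either reading nobody is barred, and Section 5.3.6 does not list these drugs as a reason for withdrawal.

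This carries weight: the literal bar is probably not what was intended. But the readings give different results. Baseline-only means no settling period at follow-up, so someone who began prophylaxis days before Year 2 would be measured; visit-anchored means a six-week delay; literal means no visit. Six centers with 11 recruitment locations (Section 5.1) could choose differently, and nothing else in the protocol decides between them.

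A reader might also infer several stronger claims that the text does not support:

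- *That only low-dose prednisone is exempt.* The same sentence exempts chronic antibiotic users from the 30-day rule; their obstacle is the following bullet.
- *That those affected can never be seen.* The antibiotic bullet binds only during therapy, and the steroid bullet, if it applies, lifts 30 days or more after stopping.
- *That higher-dose chronic steroid users are barred at follow-up.* No sentence says so, and the Table 2 limit is not among the criteria carried forward.
- *That frequent exacerbators vanish from the endpoints.* Exacerbations and deaths are captured without a visit, and it is plausible, but nowhere stated, that those starting such therapy are mainly exacerbators or in the Severe stratum.

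**Conclusion.** The antibiotic part holds as an internal contradiction. Section 5.3.1.2 applies to follow-up scheduling a window that therapy begun after baseline cannot satisfy while it continues. This conflicts with the section's own definition of a temporary criterion and with the preceding exemption. The exposure is limited to visit-based measures, of which FEV1 decline is the only primary clinical endpoint.

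The size cannot be fixed from the protocol, because no start rate is given. Lost power is minor: even assumed extra losses of 10% and 30% leave 89.0%. The more serious possibility is informative missingness of 0.01 to 0.10 SD in the Severe-stratum mean. That range rests wholly on assumed values of f and d and on sites following the text literally, so it illustrates the risk and does not predict the bias.

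The steroid part is an ambiguity only. It is unclear whether chronic prednisone at or above the Table 2 dose, begun after enrollment, defers a follow-up visit.

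**What to change.** In Section 5.3.1.2, for the Years 1, 2 and 3 visits, count the antibiotic start window back from the visit being scheduled instead of from the baseline visit. Leave the baseline wording as it is for entry.

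Separately, reconcile the 30-day bullet, its prednisone exemption and the Table 2 entry criterion, so that the protocol says in terms whether and how chronic steroid use begun after enrollment affects follow-up scheduling. Which rule to adopt is for the investigators; no dose rule is proposed here.

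The cost is about two sentences in the protocol and the clinic manual. The change concerns when visits are booked and alters nobody's treatment. The small downside is that some follow-up measurements will be taken on newly started chronic therapy. These can be flagged from the medication list collected with the medical history, which Table 3 schedules at every visit. A visit that was never held cannot be recovered at analysis.
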